8.3.1. Timing and Mechanism for Collecting Events

This table describes the timing, deadlines, and mechanism for collecting events.

Event	Collection Start	Collection Stop	Timing for Reporting to Sponsor or Designee	Mechanism for Reporting	Back-Up Method of Reporting
Adverse Event					
AE	signing of the ICF	the follow-up visit	As soon as possible upon site awareness	AE eCRF	N/A
Serious Adverse	Event				
SAE and SAE updates – prior to start of study intervention and deemed reasonably possibly related with study procedures	signing of the ICF	start of intervention	Within 24 hours of awareness	eCRF	SAE paper form
SAE* and SAE updates	start of intervention	participation in study has ended	Within 24 hours of awareness	eCRF	SAE paper form
SAE* – after participant's study participation has ended and the investigator becomes aware	After participant's study participation has ended	N/A	Promptly	SAE paper form	N/A
Pregnancy					
Pregnancy in female participants and female partners of male participants	After the start of study intervention	3 months after the last dose of study drug	Within 24 hours of learning of the pregnancy	eCRF	SAE paper form
Product Complain	Product Complaints				
PC associated with an SAE or might have led to an SAE	Start of study intervention	End of study intervention	Within 24 hours of awareness	Product Complaint Form	N/A

Event	Collection Start	Collection Stop	Timing for Reporting to Sponsor or Designee	Mechanism for Reporting	Back-Up Method of Reporting
PC not associated with an SAE	Start of study intervention	End of study intervention	Within 1 business day of awareness	Product Complaint Form	N/A
Updated PC information	_	_	As soon as possible upon site awareness	Originally completed Product Complaint Form with all changes signed and dated by the investigator	N/A
PC (if investigator becomes aware)	Participation in study has ended	N/A	Promptly	Product Complaint Form	N/A

Abbreviations: AE = adverse event; eCRF = electronic case report form; ICF = informed consent form; N/A = not applicable; PC = product complaint; SAE = serious adverse event.

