- a. Male participants:
 - Male participants with partners of childbearing potential should be willing to use reliable contraceptive methods throughout the study and for 5 half-lives of study intervention plus 90 days, corresponding to 4 months after the last injection.
- b. Female participants:
 - i. Female participants of childbearing potential (not surgically sterilized and between menarche and 1-year postmenopausal) must:
 - A. test negative for pregnancy at Visit 1 based on a serum pregnancy test.
 - B. if sexually active, agree to use 2 forms of effective contraception, where at least 1 form is highly effective, for the duration of the trial and for 30 days thereafter, and
 - C. not be breastfeeding
 - ii. Women not of childbearing potential may participate and include those who are:
 - A. infertile due to surgical sterilization (hysterectomy, bilateral oophorectomy, or tubal ligation), congenital anomaly such as Mullerian agenesis; or
 - B. post-menopausal defined as either
 - A woman at least 40 years of age with an intact uterus, not on hormone therapy, who has cessation of menses for at least 1 year without an alternative medical cause, AND a follicle-stimulating hormone >40 mIU/mL; women in this category must test negative in pregnancy test prior to the study entry

or

• A woman 55 or older not on hormone therapy, who has had at least 12 months of spontaneous amenorrhea

or

 A woman at least 55 years of age with a diagnosis of menopause prior to starting hormone replacement therapy

Informed Consent

5. Capable of giving signed informed consent as described in Appendix 1 (Section 10.1), which includes compliance with the requirements and restrictions listed in the informed consent form (ICF) and in this protocol

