7.1. Discontinuation of Study Intervention

In rare instances, it may be necessary for a participant to permanently discontinue (definitive discontinuation) study intervention. If study intervention is definitively discontinued, the participant will remain in the study to be evaluated for all planned efficacy and safety measurements. See the Schedule of Activities for data to be collected at the time of discontinuation of study intervention and follow-up and for any further evaluations that need to be completed.

Possible reasons leading to permanent discontinuation of IP:

• participant decision

o the participant requests to discontinue IP

• clinical considerations

- o initiation of GLP-1R agonist or DPP-4 inhibitor, if participants will not or cannot discontinue them
- o intolerable GI symptoms despite management as described in Section 10.8
 - *Note:* If intolerable GI symptoms persist despite symptomatic treatment, temporary drug interruption, and resumption at a lower dose of study intervention, the participant should be discontinued from the study intervention.
- o BMI ≤18.5 kg/m² with clinically significant health condition is reached at any time during the treatment period

Note: The investigator should contact the sponsor CRP and/or CRS to discuss whether it is medically appropriate for the participant to continue study treatment.

- o diagnosis of type 1 diabetes mellitus
- o diagnosis of medullary thyroid cancer after randomization
- o significant elevation of calcitonin (Section 10.4.7.3)
- o diagnosis of acute or chronic pancreatitis
- diagnosis of an active or untreated malignancy (other than basal or squamous cell skin cancer, in situ carcinomas of the cervix, or in situ prostate cancer) after randomization
- o development of any significant study intervention-related hypersensitivity reaction
- o onset of pregnancy in a female participant
- occurrence of any other treatment-emergent adverse event (TEAE), SAE, or clinically significant finding for which the investigator believes that permanent study intervention discontinuation is the appropriate measure to be taken
- o inadvertent enrollment if continued treatment with study intervention would not be medically appropriate (Section 7.2.1)
- o PHQ-9 score ≥15

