8.3.3. Pregnancy

Pregnancy (maternal or paternal exposure to study intervention) does not meet the definition of an AE. However, to fulfill regulatory requirements, any pregnancy should be reported following the SAE reporting process to collect data on the outcome for both mother and fetus.

- Abnormal pregnancy outcomes (e.g., spontaneous abortion, fetal death, stillbirth, congenital anomalies, ectopic pregnancy) are considered SAEs.
- Report Timing is provided in Section 8.3.1.

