- Total abstinence (if this is their preferred and usual lifestyle) or in a same-sex relationship with no sexual relationship with males (as part of their preferred and usual lifestyle), and agrees to maintain this status throughout trial follow-up

Note: periodic abstinence (for example, calendar, ovulation, symptothermal, and postovulation methods), declaration of abstinence just for the duration of a trial, and withdrawal are not acceptable methods of contraception

• Vasectomy – for men in clinical studies

Note: Implantable contraceptives and injectable contraceptives (such as Depo-Provera) are only permitted if started more than 18 months prior to screening. Participants should not start these methods of contraception after being enrolled in the study.

Effective Methods of Contraception (must use combination of 2 methods):

- Male condom with spermicide
- Female condom with spermicide
- Diaphragm with spermicide
- Cervical sponge
- Cervical cap with spermicide

Men, regardless of their fertility status, with nonpregnant women of childbearing potential partners must agree to either remain abstinent (if this is their preferred and usual lifestyle) or use condoms plus 1 additional highly effective (less than 1% failure rate) method of contraception (such as combination oral contraceptives, implanted contraceptives, or intrauterine device) or effective method of contraception (such as diaphragms with spermicide or cervical sponge) for the duration of the study and for 5 half-lives of study drug plus 90 days, which is approximately 4 months after the last injection. Periodic abstinence (for example, calendar, ovulation, symptothermal, and postovulation methods), declaration of abstinence just for the duration of a trial, and withdrawal are not acceptable methods of contraception.

Men with pregnant partners should use condoms during intercourse for the duration of the study and until the end of estimated relevant potential exposure in women of childbearing potential.

Men who are abstinent (if this is complete abstinence, as their preferred and usual lifestyle) or in a same-sex relationship (as part of their preferred and usual lifestyle) must agree to either remain abstinent or stay in a same-sex relationship without sexual relationships with females (usual lifestyle). In these situations, men are not required to use contraception.

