Men should refrain from sperm donation for the duration of the study and for 5 half-lives of study drug plus 90 days after the last dose of study drug, corresponding to 4 months after the last injection.

Collection of Pregnancy Information

Male participants with partners who become pregnant

- The investigator will attempt to collect pregnancy information on any male participant's female partner who becomes pregnant while the male participant is in this study. This applies only to male participants who receive study intervention.
- After obtaining the necessary signed informed consent from the pregnant female partner directly, the investigator will record pregnancy information on the appropriate form and submit it to the sponsor within 24 hours of learning of the partner's pregnancy. The female partner will also be followed to determine the outcome of the pregnancy. Information on the status of the mother and child will be forwarded to the sponsor. Generally, the follow-up will be no longer than 6 to 8 weeks following the estimated delivery date. Any termination of the pregnancy will be reported regardless of fetal status (presence or absence of anomalies) or indication for the procedure.

Female participants who become pregnant

- The investigator will collect pregnancy information on any female participant who becomes pregnant while participating in this study. The initial information will be recorded on the appropriate form and submitted to the sponsor within 24 hours of learning of a participant's pregnancy.
- The participant will be followed to determine the outcome of the pregnancy. The investigator will collect follow-up information on the participant and the neonate and the information will be forwarded to the sponsor. Generally, follow-up will not be required for longer than 6 to 8 weeks beyond the estimated delivery date. Any termination of pregnancy will be reported, regardless of fetal status (presence or absence of anomalies) or indication for the procedure.
- While pregnancy itself is not considered to be an AE or SAE, any pregnancy complication or elective termination of a pregnancy for medical reasons will be reported as an AE or SAE.
- A spontaneous abortion (occurring at <20 weeks gestational age) or still birth (occurring at ≥20 weeks gestational age) is always considered to be an SAE and will be reported as such.

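### Protocol 8.3.1 stops collecting partner pregnancies 3 months after the last dose, about a month before the male precaution period ends

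*Protocol*

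**What the plan says.** - **Collection stop.** The table in Protocol 8.3.1 has one pregnancy row for two groups: female participants, and female partners of male participants. Collection starts with study intervention and stops "3 months after the last dose of study drug". Reports are due within 24 hours of learning of the pregnancy.
- **Male precautions.** Inclusion criterion 4a (5.1) requires contraception by men with partners of childbearing potential throughout the study and "for 5 half-lives of study intervention plus 90 days, corresponding to 4 months after the last injection". Appendix 5 (10.5) gives the same period as "5 half-lives of study drug plus 90 days, which is approximately 4 months after the last injection", and applies it to sperm donation as well.
- **Partner pregnancies in Appendix 5.** Information is sought on a female partner who "becomes pregnant while the male participant is in this study".
- **Reporting rule.** Section 8.3.3 includes paternal exposure. It says that "any pregnancy should be reported following the SAE reporting process", then adds "Report Timing is provided in Section 8.3.1".
- **After the study.** The 8.3.1 table keeps a row for SAEs that the investigator learns of after participation has ended, with no stop date. Section 8.3.3 classes abnormal pregnancy outcomes as SAEs.

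**The concern.** The protocol gives the male precaution period in three places as 5 half-lives plus 90 days, about 4 months, but collects partner pregnancies for only 3. It gives no reason for the shorter stop. In the month left out, men are still asked to use contraception and not to donate sperm.

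At stake is reproductive-safety capture. Section 2.3 lists developmental safety among the known risks of increased GLP-1 receptor activity, and 8.3.3 gives the purpose of pregnancy reporting as learning the outcome for mother and child. A site told of a partner pregnancy that began in month 4, with no SAE-qualifying outcome, has no clear instruction to record it. The table also does not say whether the stop refers to when the pregnancy begins or to when the site hears of it.

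**Working it through.** **Inputs**

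- Collection stop: 3 months after the last dose (8.3.1). With an average month of 365.25 / 12 = 30.44 days, this is 91.3 days.
- Male period: 5 half-lives + 90 days, stated as 4 months (5.1, 10.5). Four average months are 121.75 days.
- Length of 5 half-lives: no half-life in days is given. Section 8.9 describes the Visit 801 sample as taken 5 half-lives after the end of treatment, and Table 3 (1.3) puts Visit 801 4 weeks after the treatment period. This implies about 28 days.

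**Reproducing the protocol's 4 months**

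28 + 90 = 118 days, and 118 / 30.44 = 3.88 months. This rounds to the stated 4.

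**Size of the gap**

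| Reading of the male period | Days | Minus 91.3-day stop |
|---|---|---|
| 28 + 90 days | 118 | 26.7 |
| 4 average months | 121.75 | 30.4 |

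The 28 days is counted from the end of treatment, while the male period runs from the last injection, so the inference is soft by up to about a week. Assuming 25 to 35 days for 5 half-lives gives 115 to 125 days, and a gap of 115 − 91.3 = 23.7 to 125 − 91.3 = 33.7 days. The conclusion of about one month does not depend on the exact half-life: 4 months less 3 months gives it directly.

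**Does another provision cover the missing month?**

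- *Appendix 5, men dosed to about Week 72.* Participation ends at Visit 801, nominally Week 76. With a last dose at Week 71 or 72, that is 5 × 7 = 35 or 4 × 7 = 28 days after it. With the 28-day extension allowed in exceptional circumstances (Appendix 14), it is 63 or 56 days. All of these precede day 91, so Appendix 5 does not reach month 4.
- *Appendix 5, men who leave soon after the last dose.* Visit 801 then follows 4 weeks after the last treatment-period visit, so the result is the same.
- *Appendix 5, men who stop drug early but stay.* Under 7.1, "the participant will remain in the study to be evaluated for all planned efficacy and safety measurements". Participation then runs on after the last dose, and Appendix 5 covers pregnancies that begin during it. The gap shrinks and, for a sufficiently early stop, disappears.
- *Section 8.3.3.* It asks for any pregnancy to be reported, but refers to 8.3.1 for timing.
- *Post-study SAE routes.* They cover SAEs, not the pregnancy itself. The post-study provision in Appendix 5 stands under female participants, is limited to SAEs judged related to study drug, and does not oblige the investigator to look for them.

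**The case against.** The best defence has three parts.

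First, 8.3.3 asks for every pregnancy to be reported, and its pointer may refer to the 24-hour reporting column of 8.3.1, not to the collection stop. That reading is possible. It makes the text ambiguous, but it does not make month 4 clearly reportable.

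Second, the outcomes of most concern are already handled, since abnormal pregnancy outcomes are SAEs and the post-participation SAE row has no stop. This stands. What remains uncovered is mainly partner pregnancies in month 4 that are ongoing or end normally.

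Third, nothing requires the collection window to equal the contraception window, and no contact is scheduled after Visit 801, so the yield will be small. This also stands and limits the importance of the point. But much of month 3 has the same weakness, and the sponsor chose to collect it.

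A reader might also infer more than the documents support:

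- *That the 3-month stop falls short only for partners of men.* The women's precaution period runs "for the duration of the trial and for 30 days thereafter", so it is tied to the trial and not to the last dose. A woman who stops drug early but stays to a nominal Visit 801 at day 504 + 28 = 532 has precautions to day 562. A 91-day stop then falls short for last doses before about day 562 − 91 = 471. The stop cannot be called sufficient for all women.
- *That 8.3.1 and Appendix 5 contradict each other for treatment completers.* One gives a collection stop and the other limits when the pregnancy begins. A pregnancy that begins in the study and is learned of later satisfies both, so the difference between the two dates is not itself an error.
- *That exact study weeks separate affected from unaffected men.* Such cut-offs would rest on the inferred 28 days and on a nominal Week 76 Visit 801. Neither is firm enough.

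**Conclusion.** The mismatch is real and minor. For men dosed to about Week 72, or who leave soon after their last dose, about the last month of the precaution period (27 to 30 days on the two readings tabulated) lies after the stated stop, and no other provision clearly covers it. The figure in days assumes about 28 days for 5 half-lives; the figure of about one month needs only the protocol's own 3 and 4 months.

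No count of missed pregnancies is possible, because the documents do not give the number of men with partners of childbearing potential. Efficacy, alpha and power are unaffected. This is a worthwhile clarification, not a threat to the trial.

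**What to change.** In 8.3.1, give female partners of male participants their own row. Collect any pregnancy that begins from the start of study intervention until the later of:

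- the end of the man's study participation, or
- 5 half-lives plus 90 days (about 4 months) after his last dose.

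Make it reportable within 24 hours of the site learning of it, whenever that is. Use the same onset period in the partner paragraph of Appendix 5. Defining the window by onset also settles how to treat pregnancies recognised late. The male contraception and sperm-donation periods need no change. This proposal takes no position on the stop for female participants.

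The cost is wording in two places and a slightly longer passive reporting period, with no added visit or assessment. After Visit 801, detection still depends on the man telling the site.

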8.3.2. Medical Device Incidents (Including Malfunctions)

Medical devices are being used in this study for the purposes of administering tirzepatide. In order to fulfill regulatory reporting obligations worldwide, the investigator is responsible for the detection and documentation of events meeting the definitions of incident or malfunction that occur during the study with such devices.

The definition of a medical device incident can be found in Section 10.9 (Appendix 9).

Note: Incidents fulfilling the definition of an AE/SAE will also follow the processes outlined in Section 8.3.1.

8.3.2.1. Time Period for Detecting Medical Device Incidents

- Medical device incidents, or malfunctions of the device that result in an incident, will be detected, documented, and reported to the sponsor during all periods of the study in which the medical device is used.
- If the investigator learns of any incident at any time after a participant has been discharged from the study, and such incident is considered reasonably related to a medical device used during the study, the investigator will promptly notify the sponsor through the complaints process.

The method of documenting medical device incidents is provided in Section 10.9 (Appendix 9).

8.3.2.2. Follow-Up of Medical Device Incidents

- All medical device incidents involving an AE will be followed and reported in the same manner as other AEs (see Section 8.3.1). This applies to all participants, including those who discontinue study intervention.
- The investigator is responsible for ensuring that follow-up includes any supplemental investigations as indicated to elucidate the nature and/or causality of the incident.
- New or updated information will be recorded on the originally completed form with all changes signed and dated by the investigator.

8.3.2.3. Prompt Reporting of Medical Device Incidents and Malfunctions to Sponsor

- Medical device incidents or malfunctions will be reported to the sponsor within a
 business day or as determined for the study, after the investigator determines that the
 event or issue meets the protocol definition of a medical device incident or
 malfunction.
- Medical device incidents or malfunctions that result in an SAE will be reported to the sponsor within 24 hours, in the same manner as other SAEs.
- Malfunctions will be reported via the Product Complaint Form and sent to the sponsor per training and per instructions provided on the Product Complaint Form.
- The same individual at the site will be the contact for the receipt of medical device reports and SAEs.

8.3.2.4. Regulatory Reporting Requirements for Medical Device Incidents

- The investigator will promptly report to the sponsor all incidents occurring with any
 medical device provided for use in the study in order for the sponsor to fulfill the
 legal responsibility to notify appropriate regulatory authorities and other entities
 about certain safety information relating to medical devices being used in clinical
 studies.
- The investigator, or responsible person according to local requirements (for example; the head of the medical institution), will comply with the applicable local regulatory requirements relating to the reporting of incidents to the Institutional Review Board (IRB)/Independent Ethics Committee (IEC).

8.3.3. Pregnancy

Pregnancy (maternal or paternal exposure to study intervention) does not meet the definition of an AE. However, to fulfill regulatory requirements, any pregnancy should be reported following the SAE reporting process to collect data on the outcome for both mother and fetus.

- Abnormal pregnancy outcomes (e.g., spontaneous abortion, fetal death, stillbirth, congenital anomalies, ectopic pregnancy) are considered SAEs.
- Report Timing is provided in Section 8.3.1.

8.4. Treatment of Overdose

Study drug overdose (more than the specified number of injections) will be reported as an AE. In the event of overdose, refer to the Investigator's Brochure for tirzepatide.

8.5. Pharmacokinetics

Pharmacokinetic samples should be collected prior to the dose administration and at the same time as the immunogenicity sample. Population PK and PD parameters may be derived. Relationship between tirzepatide exposure and safety, tolerability and efficacy measures may be explored.

8.6. Pharmacodynamics

The area under the curve from 0 to 2 hours (AUC[0-2h]) for glucose and insulin during an OGTT will be calculated using the trapezoidal rule. The AUC(0-2h) as well as other derived parameters or observed concentration at specific time points for each participant on the study day will also be baseline-adjusted. The concentrations on Day -1 will be used as baseline.

